#### STUDY SUMMARY

Study Title	Utility of 3-dimensional gait analysis in reference to clinical assessments to detect significant change after a cerebrospinal tap test in patients investigated for idiopathic normal pressure hydrocephalus
Internal ref. no. (or short title)	Utility of 3D gait analysis in iNPH
Study Design	Cross-sectional, controlled study
Study Participants	People with iNPH and healthy control participants
Planned Size of Sample (if applicable)	20 people with iNPH 20 healthy volunteers of similar age and sex distribution
Follow up duration (if applicable)	N/A
Planned Study Period	12 months
Research Question/Aim(s)	We aim to provide a detailed characterization of gait impairment in people with idiopathic normal pressure hydrocephalus (iNPH) to aid diagnosis and provide a platform for future work to objectively assess the effectiveness of treatment interventions using gait analysis variables as the main outcome measure. Our primary objective is to identify key gait and balance variables that can objectively characterize the mobility impairment in iNPH and that will also serve as measures to accurately quantify changes in mobility and balance before and after lumbar puncture to remove cerebrospinal fluid (CSF tap test or TT), a standard clinical procedure to assess whether patients may benefit from permanent treatment with a neurosurgical operation to drain CSF (shunt). Whilst the emphasis will be placed on objective laboratory-based measures, this work will also seek

to validate robust clinical measures to support clinic-based assessments as potential surrogate measures and for instances where sophisticated gait analysis may not be accessible. We hypothesize that (i) those with iNPH will exhibit decreased gait velocity (slower walking), increased step width variability, unsteadiness (increased centre of mass trajectories), reduced joint ranges of motion, and poorer balance test scores, when compared to age-matched controls; (ii) gait outcome variables will improve following tap test; and (iii) gait analysis will be more sensitive than clinical
controls; (ii) gait outcome variables will improve following tap

#### ROLE OF STUDY SPONSOR AND FUNDER

Northern Care Alliance NHS Foundation Trust (NCA) is the sponsor of the study. The Hydrocephalus Association (HA), USA, is the funder of the study. The clinical research team is based at the NCA. The academic research teams are based at the Manchester Metropolitan University (MMU) and Gothenburg University (GU), Sweden. The clinical and academic research teams were solely responsible for the design of the study and manuscript writing and will be solely responsible for the data analysis and interpretation and dissemination of the results. The sponsor will ensure that the study conduct adheres to NHS standards.

# ROLES AND RESPONSIBILITIES OF STUDY MANAGEMENT COMMITEES/GROUPS & INDIVIDUALS

We have consulted a group of patients and carers living with iNPH for their views on the purpose of the study, and its accessibility, in terms of the potential burden of participating and the ease of understanding the participant information sheets. Their feedback was invaluable, and they expressed keen interest and gratitude for such a study given the significant impact the condition has on their quality of life.

#### PROTOCOL CONTRIBUTORS

The researchers of this study are the sole contributors to study design, data analysis and interpretation, manuscript writing and dissemination of results.

The sponsor's role and responsibility is to ensure that the study conduct adheres to NHS research standards. The funder's role and responsibility is to assess the study for scientific validity and funding.

KEY WORDS:	idiopathic normal pressure hydrocephalus, iNPH, gait
	analysis, outcome measure, CSF tap test

**STUDY FLOW CHART** 

See appendix

# 1 BACKGROUND

Idiopathic normal pressure hydrocephalus (iNPH) is a progressive condition of gait, bladder and cognitive dysfunction(1). Results from prevalence studies indicate that around 2% of people aged 65 or above suffer from iNPH. Mean age is around 74 years, the majority of patients being in their 70ies and there is a slight male predominance (2). Demonstration of change in patients' mobility is crucial to inform diagnostic and therapeutic decisions at the stage of diagnosis and on follow-up after treatment (3). Current practice relies on manual mobility assessments such as the Tinetti gait and balance assessment tool, but changes can be difficult to detect, e.g., if gait is only mildly impaired or change is discrete. Furthermore, while video-recorded gait performance is often used before and after drainage of excess fluid during lumbar puncture (LP, "CSF taptest"), there is no universally accepted, standardised rating system (4). The test is therefore often rated as "improvement" or "no improvement". Literature reports of the CSF taptest vary in methodology and many reports are outdated. Few studies have used advanced gait analysis techniques for identification and monitoring of people with iNPH - of those that have, none has reported analyses - which include joint kinetics and kinematics, instead only reporting simple outcome measures that could be obtained through more rudimentary techniques (5-8). Therefore, there is a clear unmet need for a more sensitive gait analysis method to identify changes in mobility in people with iNPH. We believe this work will be the first to (i) provide a complete, detailed characterization of gait impairment in patients with iNPH compared to healthy controls using 3D gait analysis; (ii) identify and quantify changes after LP in gait in reference to standard clinical assessments; and (iii) explore thresholds to differentiate responders from nonresponders to LP compared to standard clinical assessment methods with the aim of providing an objective reliable primary outcome variable for future randomised controlled clinical trials and to improve routine clinical care of patients. We therefore expect the outcomes of this work to inform future clinical care guidelines and further research into better diagnosis and treatment of people with iNPH.

# 2 RATIONALE

Currently, the comparison of suspected prevalence in epidemiological studies and the recorded number of treatments per year suggests that the condition is largely under-recognized in the world (9). This under-recognizion of iNPH leads to continued suffering in many of those who are never diagnosed. We believe that the proposed project is both innovative and pioneering: in this first proof-of-concept study we aim to use advanced 3D gait analysis, which has not been used before in this context, to identify and quantify gait parameters typical for iNPH. Such methods could prove more sensitive at capturing changes when evaluating effects of CSF drainage procedures and at monitoring the efficacy of the permanent treatment, the surgical placement of a small plastic tube (shunt) draining fluid out of the fluid filled space in the brain (ventricle) into the abdomen (peritoneum), a VP shunt, than routine clinical assessments. It may also help to identify which individual or combination of clinical markers are most useful in the absence of 3D gait analysis. If they increased the sensitivity of the Tap Test to select candidates for shunt surgery, this would help avoid missing potential patients who should be offered treatment. Furthermore they could pick up early any deterioration in shunted patients or help document an improving trajectory after shunting.

In consultation with people with iNPH and their carers, both within the service and as part of a formal Patient & Public Involvement exercise, they have reported a significant toll of the condition on their quality of life. They were grateful that the condition was being studied and hoped to support any research which would improve understanding of iNPH. Studying a condition which affects the elderly is particularly important as many in this patient group feel forgotten about. In some cases, they feel as if their ailments are attributed to age-related changes, and hence are of less importance to healthcare providers. In conducting this research, we hope to improve awareness and understanding of the condition, and also the quality of lives of people with iNPH and their carers

\*Sponsor's representative: [name], Managing Director of Research & Innovation Northern Care Alliance NHS Foundation Trust, [name] email: [contact]

# **3 THEORETICAL FRAMEWORK**

iNPH is a clinical syndrome consisting of prominent and progressive decline in mobility followed by less prominent but equally progressive decline in bladder function and cognition derived by analogy from NPH (1, 10) and distinguished from it by the absence of a preceding insult such as meningitis or subarachnoid haemorrhage, in the context of obligatory ventriculomegaly on brain imaging. The symptoms may improve by draining cerebrospinal fluid with a surgically inserted "shunt" (11). To evaluate the likelihood of shunt responsiveness people with iNPHs' mobility is assessed before and after lumbar puncture draining a large volume of CSF (3), eg 50mls, mimicking the permanent procedure, for any indication of improvement. If improvement can be demonstrated probabilities of permanent improvement following CSF shunting is quoted at 80%. Demonstrating change, ie rating the tap test as positive or negative is challenging because there is no agreement on what assessments are best, how they should be used (4) and how to interpret the results if change is small because of a good baseline or discreet change. 3-dimensional gait analysis is a highly sophisticated laboratory technique providing objective quantitative measures of mobility combining the absence of operator dependence and high resolution enabling the demonstration of minute numeric change. It offers the opportunity to quantitatively characterise a neurological gait disorder (as opposed to the qualitative characterisation provided by the neurological examination, eg into "spastic", "frontal" or "ataxic") which has the advantage, again, of quantifying change (as opposed to the qualitative neurological examination which tends to remain unchanged albeit potentially "less severe") and is in that respect similar to assessment scales such as the Tinetti gait and balance scale which calculates a score but its role in the tap test is not universally accepted. We will compare clinical mobility assessments with 3D in an attempt to validate a combination of clinical markers providing maximum discrimination between before and after.

# 4 RESEARCH QUESTION/AIM(S)

We aim to provide a detailed characterization of gait impairment in people with iNPH to provide a platform for future work to objectively assess the effectiveness of treatment interventions using gait analysis variables as the main outcome measure. We have experience identifying a selection of these variables as evidence of movement impairment from our extensive research with other clinical populations.

## 4.1 Objectives

Our primary objective is to identify key gait and balance variables that can objectively characterise the mobility impairment in iNPH and that will also serve as measures to accurately quantify changes in mobility and balance before and after lumbar puncture to remove cerebrospinal fluid (CSF tap test or TT), a standard clinical procedure to assess whether patients may benefit from permanent treatment with a shunt. Whilst the emphasis will be placed on objective laboratory-based measures, this work will also seek to validate robust clinical measures to support clinic-based assessments as potential surrogate measures and for instances where sophisticated gait analysis may not be accessible. We hypothesise that

- those with iNPH will exhibit decreased gait velocity (slower walking), increased step width variability, unsteadiness (increased centre of mass trajectories), reduced joint ranges of motion, and poorer balance test scores, when compared to age-matched controls;
- (ii) gait outcome variables will improve following tap test; and
- (iii) in view of the low negative predictive value but high specificity of the TT gait analysis will be more sensitive than clinical assessments at demonstrating change.

Secondary characterization objectives will aim to quantify general levels of everyday activity with a fitbit, psychological factors such as mood and levels of anxiety, quality of life and carer burden (the latter in patients only), and expectations and experience of gait analysis in healthy control participants and people with iNPH. We hypothesize that general levels of mobility (i.e. in everyday activity) will increase following TT; psychological factors (e.g. mood, expectations) may be considered as potential confounding, mediating and response variables.

## 4.2 Outcome

The primary outcome measures of the 3D gait analysis are the 'dynamic balance' that evaluates the movement (sway) in the body centre of mass relative to the centre of pressure under the feet, step length, gait velocity and temporo-spatial measures of gait variability.

The discriminant performance between groups and the screening characteristics for shunt surgery of gait analysis variables will be compared with those of the current standard clinical assessments. These include: 10m timed walk (number of steps and seconds), 360 degree timed turns (number of steps and seconds), Tinetti gait and balance assessment (score out of 28), timed up and go test (seconds), 6m walk test (minutes and seconds), single leg stand (seconds), Romberg test(seconds).

Secondary outcome measures quantify general levels of everyday activity with a fitbit, levels of anxiety and depression with the hospital anxiety and depression scale (HADS, score out of 21), quality of life with the EQ 5D 5L and carer burden with the Burden Scale for Family Caregivers questionnaire (patients only), and the experience of gait analysis in controls and people with iNPH before and after TT in a semi quantitative interview.

## 5 STUDY DESIGN and METHODS of DATA COLLECTION AND DATA ANALYIS

This pilot study will obtain data necessary to estimate the sample size for a large-scale, pivotal randomized controlled trial, including characterization of gait and balance data for patients with suspected iNPH. We will also obtain 1) estimate of variability of the follow-up and change scores on primary outcome measures; 2) correlation between baseline and follow up scores (r value); and 3) smallest clinically meaningful between-group effect for the primary outcomes.

We will use a 16-camera 3-dimensional motion analysis system to accurately track the movement of markers positioned on specific anatomical landmarks of each participant's body while walking. Force plates embedded in a bespoke floor-mounted walkway will provide accurate measurements of ground reaction forces under the feet as the participant walks across them. These measures will provide a detailed understanding of the movement of the limbs and whole body, and the rotational forces developed around all lower limb joints. We also have the ability to record muscle activity through surface electromyography, which provides insight into when, and by how much, muscles are being utilised to perform a task. We will examine gait with a range of support conditions (e.g. with natural use of preferred walking aid if required; with assistance from partner/carer/researcher; with use of a standardised minimal walking aid such as a cane/stick; and without any assistance if possible) to allow appropriate comparison against controls and pre-post treatment. Static balance will be examined through quiet stance (e.g. 30s standing on force plates; centre of pressure and centre of mass trajectories and their time derivatives to be analysed), and dynamic balance examined during gait. Continuous data sets will be generated and used to quantify different aspects of gait and balance function.

Gait variables of interest: The research team have extensive experience of investigating clinical movement impairment across a range of other clinical conditions including diabetes, stroke and Parkinson's disease. While measuring the full range of detailed gait variables, based on our experience and evidence from the literature, we hypothesise analysis may focus around some key variables. These include a measure of 'dynamic balance' that evaluates the movement (sway) in the body centre of mass relative to the centre of pressure under the feet, shown to be a sensitive measure of gait impairment in diabetic neuropathy (12). Other variables of focus based on previous research include step length, gait velocity and temporal-spatial measures of gait variability (13-15). Based on the team's clinical experience of iNPH gait and from our recent Patient and Public Involvement (PPI) sessions in preparation for this project, patients tell us they sometimes experience the feeling of their feet "sticking to the floor" and in this respect we hypothesise that the temporal-spatial gait variables (reflecting timing and distance of gait) events might be particularly pertinent.

Remote physical activity monitoring devices (Fitbits) will be supplied to all participants (patients and controls) when they attend for their first visit to the gait laboratory. Patients start monitoring their activity levels 7 days prior to their lumbar puncture until 7 days post-lumbar puncture; patients and controls will be asked to record the amount of daily activity during this time period. Controls will monitor their activity in the 7 days pre- and 7 days post-gait assessment. To mitigate any effects of the initial wearing of the monitor (i.e. gait-related changes), only the data from the final 3 days of the pre-LP (or gait assessment for controls) and 7 days post will be analysed.

Psychological factors will be monitored in patients (part of the clinical routine) and controls (when they attend the gait laboratory) using the Hospital Anxiety and Depression Scale. Quality of life will be assessed with the EQ-5D-5L patient version (patients -part of the clinical routine- and controls when they attend the gait laboratory) and EQ-5D-5L proxy versions (patients only, part of the clinical routine) and carer burden will be assessed with the Burden Scale for Family Caregivers (patients only, part of the clinical routine). These secondary assessments will provide insight into clinically-relevant outcomes of everyday activity in the period immediately following tap-test and may be relevant for the participants' performance. We will also evaluate participants' experience and expectations of their gait and balance performance pre and post tap test when measured clinically and with gait analysis, assessing for concordance and participants' reaction to the results using a questionnaire. Patients are followed closely after the TT as part of clinical routine to discuss the results and plan further management.

Key gait and balance variables that can be used to characterize iNPH will be determined through the use of logistic (discriminant) regression analyses between patients and healthy controls. Given the sample size of this

initial study, variables will be considered unifactorially. A similar approach will be used to estimate the Receiver Operating Characteristic (ROC) curve for these variables as screening tools for shunt surgery. Standardised effect sizes for the key gait and balance variables will be compared informally with those derived for currently routine clinical measures by repeating the above analyses.

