#### 7.1.2 Exclusion criteria

Excluded are participants with

Other confirmed medical or surgical conditions better explaining symptoms than iNPH (patients) or with substantive impact (eg Parkinson's, osteoarthritis) as judged by the investigators (patients and control)

Secondary or obstructive hydrocephalus; previous surgical procedures for hydrocephalus (patients)

Amputation of lower limb/appendages

Musculoskeletal injury/recent lower-limb surgeries affecting gait or other musculoskeletal ailments affecting gait and balance performance as judged by the investigators.

Participants on specific medications (eg centrally acting) better explaining symptoms than iNPH (patients) or with substantive impact as judged by the investigators (patients and control)

Unable to carry out all study procedures.

Unable to comprehend informed consent.

- 7.2 Sampling
- 7.2.1 Size of sample

20 males and females with iNPH.

20 unmatched healthy volunteers of similar age and sex distribution.

We have determined the target sample size in anticipation that several gait variables will show complete discrimination between patients and controls and to develop preliminary estimates of variation (SD) in follow-up values and change scores following TT. We will also derive initial estimates of performance characteristics, such as area under ROC curve, for use of gait variables to screen for shunt surgery. Given the preliminary aims and multiplicity of candidate gait variables at this stage, all statistical significance values will be interpreted as indicative rather than definitive and no statistical power calculation would be appropriate

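### Key gait variables are to be chosen on patient-versus-control discrimination alone, although the primary objective also requires them to quantify change over the tap test

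*Protocol*

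**What the plan says.** Section 4.1 states one primary objective with two parts. The study is to "identify key gait and balance variables that can objectively characterise the mobility impairment in iNPH", and those variables "will also serve as measures to accurately quantify changes in mobility and balance before and after lumbar puncture". Hypothesis (ii) expects gait variables to improve after the tap test. Hypothesis (iii) expects gait analysis to be more sensitive than clinical assessment at showing change.

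Section 5 gives the analysis: "Key gait and balance variables that can be used to characterize iNPH will be determined through the use of logistic (discriminant) regression analyses", with patients compared with healthy controls and each variable taken singly because of the sample size. ROC curves for shunt surgery are to be estimated for these variables by a similar approach. Standardised effect sizes for the key variables are then compared informally with those of the routine clinical measures, by rerunning the same analyses.

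Change scores appear elsewhere. Section 6 explains that the second patient visit exists to obtain them. The opening of section 5 and section 7.2.1 use them to estimate variability and the baseline-to-follow-up correlation. Section 1 names the intended product as a reliable primary outcome variable for later randomised trials.

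**The concern.** The objective sets two conditions and the stated selection analysis examines one. A variable can mark the disease strongly and still not move when CSF is drained. Such a variable may help diagnosis, but it cannot serve as the endpoint of a treatment trial, which is the use that section 1 has in view.

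The same gap affects hypothesis (iii). A comparison of patient-control effect sizes between gait analysis and clinical tests shows which method better separates patients from healthy people. It does not show which better detects change within patients.

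**Working it through.** **Reproduction.** There is no planned figure to reproduce. Section 7.2.1 declines a power calculation, and the protocol states no alpha, effect size or SD. The check is therefore mainly one of reading.

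**Where could a change criterion come from?**

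| Place in protocol | Use of tap-test change | Selects gait variables on change? |
|---|---|---|
| 3, Theoretical framework | Before/after discrimination for a combination of clinical markers | No |
| 4.1, hypothesis (ii) | Improvement expected | No analysis attached |
| 4.2, Outcome | Primary outcomes listed with no contrast; group discrimination and shunt screening compared with clinical tests | No |
| 5, opening | Variability of change scores; baseline/follow-up correlation | No |
| 5, variables of interest | Expected focus of analysis | No |
| 5, analysis | "determined through the use of logistic (discriminant) regression analyses between patients and healthy controls" | No |
| 5, ROC | Shunt surgery, for the same variables; not said to use change scores | No |
| 6, Study setting | Change score collected | No |
| 7.2.1, Size of sample | SD of follow-up values and change scores | No |

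The data for a change criterion will exist, but no section uses them to choose variables or to compare gait analysis with clinical tests.

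**Why discrimination cannot stand in for response.** Every variable that separates the groups completely has an AUC of 1, so AUC cannot rank such variables at all, let alone by response.

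**Illustration.** Assumptions not in the protocol: normal data, and two-sided 5% used only as a yardstick. Let d be the patient-control difference in SDs, δ the mean tap-test change in baseline SDs, and r the baseline-to-follow-up correlation.

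- *Between groups, 20 v 20:* AUC = Φ(d/√2); noncentrality = d√(20/2) = 3.162d on 38 df.
  - d = 1.0: AUC 0.76, power 87%
  - d = 1.5: AUC 0.86, power 99.6%
  - d = 2.0: AUC 0.92, power 100% to the nearest tenth
- *Paired change, 20 patients:* dz = δ/√(2(1−r)); noncentrality = dz√20 on 19 df.
  - δ = 0: 5% whatever r is
  - δ = 0.3, r = 0.5: dz = 0.30, power 25%
  - δ = 0.3, r = 0.7: dz = 0.39, power 38%
  - δ = 0.3, r = 0.9: dz = 0.67, power 81%

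The first set depends only on d and the second only on δ and r. A simulation of a variable with no true change (r = 0.7, 20,000 runs) gave:

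| d | Patient-control difference detected | Both contrasts detected | Groups completely separated |
|---|---|---|---|
| 1.0 | 86.4% | 4.1% | 0.0% |
| 1.5 | 99.7% | 5.3% | 0.03% |
| 2.0 | 100% | 4.8% | 0.4% |

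Complete separation is rare even at d = 2.0. The expectation in section 7.2.1 therefore implies still larger differences under normality, where patient-control comparison is saturated.

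**Precision of the proposed estimate.** SE(dz) ≈ √(1/20 + dz²/40).

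- dz = 0.3: √(0.05 + 0.00225) = 0.229; 95% CI 0.3 ± 0.45, or −0.15 to 0.75.
- dz = 0.6: √(0.05 + 0.009) = 0.243; 95% CI 0.6 ± 0.48, or 0.12 to 1.08.

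**The case against.** The strongest reply is that the section 5 sentence is limited to variables that characterise iNPH. For that purpose patients versus controls is the right contrast, and the sentence does not claim that a variable passing it responds to the tap test. This stands, and the sentence is not wrong in itself. But the later effect-size comparison is made for the variables so chosen and by the same analyses, so the second half of the objective is left with no part in the selection.

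A statistical analysis plan could add a change criterion, and the test details would properly belong there. The point rests on something narrower: the protocol fixes an analysis that does not match its own objective and hypothesis (iii).

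This is also a pilot in which "all statistical significance values will be interpreted as indicative rather than definitive". That disposes of any complaint about error control, and a reader who infers inflated false-positive risk across outcomes and contrasts would be pressing a claim that the study does not make. It does not settle which variables are called key.

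Other stronger readings also fail:

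- *That the objective could be declared met on either contrast.* Section 4.1 joins the two properties, so one alone would not meet it.
- *That a known share of the key variables will be unresponsive.* Any such share only returns what is assumed about the candidates, and the protocol gives no p-value cut-off for selection.
- *That the primary outcomes contradict hypothesis (i).* A hypothesis may name measures that are not primary outcomes, and most of the primary outcomes correspond to items in it.
- *That one lead variable must be named.* That would sit badly with a study meant to identify variables.

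Finally, a strict two-test rule at 20 pairs would discard responsive variables. Section 1 also expects responders and non-responders, whose changes a group mean blends. Both are reasons for judging on estimates and intervals.

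**Conclusion.** The point holds as a mismatch between objective and analysis. As written, the plan selects key variables, and compares gait analysis with clinical tests, without using the post-minus-pre change that the primary objective and hypothesis (iii) concern. It should be corrected, but it does not undermine the study's data or its between-group findings.

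The textual finding needs no assumption. The 86% to 100% detection rates for an unresponsive variable rest on normal data, a 5% yardstick, r = 0.7 and differences of 1.0 to 2.0 SD. They show that discrimination carries little information on response and do not forecast this study's results. If impairment and response happen to go together across variables, the practical harm would be smaller. The protocol gives no figure on that relation.

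**What to change.** Amend the analysis paragraph of section 5 in three places.

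1. For every candidate gait variable and every clinical test, estimate the paired standardised post-minus-pre change in patients with its 95% CI. Use the same standardiser throughout (for example the SD of the change) and state the direction that counts as improvement.
2. For the primary objective, name as key those variables judged on two estimates together: patient-control discrimination (AUC or standardised effect size, with CI) and the paired change in the hypothesised direction. Apply no strict p < 0.05 rule to either.
3. Make the gait-versus-clinical comparison for hypothesis (iii) on the paired standardised change. Keep the patient-control comparison for characterisation.

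The cost is protocol wording and one paired analysis of data already planned, with no extra participants or visits. Fewer variables will be called key, and with 20 pairs some truly responsive ones will have wide intervals, as the calculation above shows.

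### The protocol expects several gait variables to separate the groups completely, yet names a logistic regression that, fitted by maximum likelihood, has no finite estimate in that case

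*Protocol*

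**What the plan says.** Protocol section 7.2.1 (Size of sample) plans "20 males and females with iNPH" and "20 unmatched healthy volunteers of similar age and sex distribution". It gives no effect size, SD, alpha or power. Its first reason for the size reads: "We have determined the target sample size in anticipation that several gait variables will show complete discrimination between patients and controls". Its second is to obtain preliminary SDs for follow-up values and change scores after the tap test. It adds that "all statistical significance values will be interpreted as indicative rather than definitive and no statistical power calculation would be appropriate".

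Protocol section 5 says that the key gait and balance variables "will be determined through the use of logistic (discriminant) regression analyses between patients and healthy controls", and that, because of the sample size, "variables will be considered unifactorially". It continues: "A similar approach will be used to estimate the Receiver Operating Characteristic (ROC) curve for these variables as screening tools for shunt surgery". After that, the key gait variables' standardised effect sizes are to be compared informally with those of the routine clinical measures, which are obtained by running the same analyses on the clinical measures.

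Neither section names an estimator, a penalty, a test or a selection rule for the logistic model, and neither says what is reported when a variable separates the groups completely.

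**The concern.** Complete discrimination by one continuous variable means that every patient lies on one side of some cut-off and every control on the other. In that case the logistic likelihood keeps rising as the slope grows, so no finite maximum-likelihood estimate exists. The protocol expects this for several variables, and they are the ones that the study most hopes to find.

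The primary objective (section 4.1) is to identify key gait and balance variables, and this regression is the only method named for doing so. Section 4.2 also promises to compare the discriminant performance of gait variables with that of the clinical assessments. If the effect size comes from the logistic slope, the best gait variables would have no usable value to set beside each other or beside a clinical test.

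**Working it through.** **Inputs.** From section 7.2.1: 20 patients, 20 controls, complete discrimination anticipated for several variables. From section 5: logistic regression with one predictor per model. The standardised patient-control difference d is not in the protocol. Here it is an **assumption**, varied from 2 to 6 SD with normal data and equal SDs. The figure of 20 + 20 cannot be reproduced, because no power calculation was made.

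**1. Estimate under complete separation.** With one predictor, the log-likelihood is the sum of log p over patients and log(1 − p) over controls. Put the cut-off between the groups and let the slope grow: each fitted probability tends to 1 for patients and 0 for controls, and the log-likelihood tends to its upper bound of 0. No finite slope reaches that bound.

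**2. What software prints.** One separated 20 v 20 data set was fitted by two standard maximum-likelihood routines:
- first routine: slope 53, SE 9.9 × 10^12, Wald p = 1.00;
- second routine: slope 22.9, SE 13,560, Wald p = 0.999.

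The data and the model are the same. The slopes differ because each routine stopped at a different point.

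**3. Other tests on separated data.**
- Likelihood ratio: the null log-likelihood is 40 × ln(0.5) and the limiting model log-likelihood is 0. Chi-square = 2 × 40 × ln 2 = 55.45 on 1 df, p = 9.6 × 10^-14.
- Exact Mann-Whitney at AUC = 1: p = 2 / C(40,20) = 2 / 137,846,528,820 = 1.5 × 10^-11.

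The evidence of a difference is overwhelming. Only the slope and its Wald inference break down.

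**4. How often separation occurs, and Wald p-values near it.** Simulation of 20 v 20: 4,000 data sets per d for the chance of separation, of which 600 were fitted.

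| Assumed d (SD) | P(complete separation) | Not separated: share with Wald p > 0.05 |
|---|---|---|
| 2 | 0.3% | 1% |
| 2.5 | 3% | – |
| 3 | 16% | 18% |
| 3.5 | 41% | 28% |
| 4 | 66% | 52% |
| 5 | 94% | 75% (few runs) |
| 6 | 99.7% | – |

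A repeat with 20,000 data sets per d gave 0.5%, 3.7%, 16%, 39%, 65%, 95% and 99.6% for the middle column. In separated runs the Wald p-value was never below 0.78. In runs without separation, for d of 3 or more, the likelihood-ratio p-value was always below 10^-6, although the Wald p-value worsened as discrimination improved.

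**5. Penalised fit.** Firth logistic regression gave a finite slope throughout. For d = 3 to 6 the largest penalised likelihood-ratio p-value was about 2 × 10^-6. Median slopes per within-group SD were 2.61 (d = 3), 2.67 (3.5), 2.48 (4), 1.91 (5) and 1.47 (6). For normal data with equal SDs the true slope per SD equals d, so shrinkage is modest at d = 3 (2.61 against 3) and heavy at d = 6 (1.47 against 6). The Firth slope therefore falls as separation widens, and it should not be used to order variables.

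**The case against.** The protocol does not say that the fit is ordinary maximum likelihood. Its wording, logistic with discriminant in brackets, does not exclude a penalised fit or a linear discriminant analysis, and an analysis plan that is not shown may settle this. That stands as a limit on the point: the failure is conditional on a standard fit. It does not remove the conflict, because the protocol names both the method and the scenario in which that method, fitted in the usual way, gives no estimate.

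A reader might infer that the best variables would necessarily look non-significant and rank below weaker ones. The documents do not support this. No Wald test is specified, the likelihood-ratio test of the same model points strongly the other way, no significance threshold governs selection, and nothing says that variables are ranked by p-value.

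A reader might also infer that the AUC intervals would collapse to a point. No interval method is named, and section 5 ties the ROC curves to screening for shunt surgery, whereas the expectation of complete discrimination concerns patients against controls. Nor does section 7.2.1 claim any certainty about sensitivity that would need correcting; it calls its outputs preliminary and initial.

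Two more points for the plan stand. Standardised mean differences and AUC exist under separation, so an effect size not taken from the slope would survive, although AUC ties at 1 for every separating variable. And estimating the SDs of follow-up and change scores, the other reason for the sample size, is untouched.

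**Conclusion.** The point holds in a conditional form. On the protocol's own expectation, the method named in section 5 would, under standard maximum likelihood, give no finite slope and no usable Wald interval for the variables that discriminate completely. Slope-based effect sizes for those variables could not be compared with each other or with the clinical tests.

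The internal conflict does not depend on d, since complete discrimination is the protocol's stated premise. How often it would arise does: from below 1% at 2 SD to over 99% at 6 SD, assuming normal data with equal SDs. The weight is moderate. This is a pilot, its p-values are declared indicative, separation is visible to the analyst, and the remedy needs no change to design or data collection.

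**What to change.** In section 5, state that each variable is analysed by Firth penalised-likelihood logistic regression per 1 SD (naming the SD, for example the pooled within-group SD), with profile penalised-likelihood confidence intervals and p-values. State also that gait and clinical variables are compared by standardised mean difference and by patient-versus-control AUC, each with a confidence interval, using an AUC interval method that does not collapse when the observed AUC is 1. The standardised mean difference is needed beside the AUC because it still orders variables that tie at AUC = 1. The Firth slope should not serve for ordering, for the reason shown in the working. If linear discriminant analysis was meant, the section should say so.

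The cost is one or two sentences and standard software, with no extra participants or measurements. The statistical price is shrinkage of the slope, modest away from separation and marked when separation is wide.
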